5.0 DOCUMENT HISTORY

Document	Date of Issue	Summary of Change
Protocol Version 2.1	03.02.2013	1. Defined walking speed removed from inclusion criteria 2. Additional questionnaire on upper limb function added (AMSQ).
Protocol Version 2.0	28.03.2012	Formatted IMB specification
Original Protocol	02.01.2012	Not applicable

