with spinal cord injury, may be broadly categorized as excitatory effects in the nervous system consistent with the K⁺ channel blocking activity of the compound in the nervous system. These AEs include dizziness, paresthesias, insomnia, balance disorders, anxiety, confusion, and seizure. In studies in MS patients, the following most frequent treatment-related AEs were also observed: urinary tract infection, asthenia, back pain, constipation, dyspepsia, and pharyngolaryngeal pain. At higher dose levels, more severe central nervous system AEs such as confusion and seizure have been seen. With the adoption of the 10 mg BID dose in extension studies, the rate of first seizure has been approximately 0.32 per 100 subject-years. This rate does not exceed the expected incidence of seizures in the MS population, particularly in the more advanced disease state with significant ambulatory disability¹⁸. However, patients were excluded from these studies if they had a history of seizure or evidence of epileptiform activity on a screening electroencephalogram. Seizures have been seen in the post marketing setting in the US although confounding factors such as seizure history and use of concomitant medications that have been associated with a seizure risk may have contributed to the occurrence of seizures in some patients. No new safety signal has been detected as of March 2011.

The FDA has recently approved Fampridine, a slow release preparation, for use in the MS patient population.⁸ It has also recently been approved in Europe (20th July 2011).¹⁷ Most studies of fampridine assessed timed walking over twenty-five feet and the Multiple Sclerosis Walking Scale-12 (MSWS-12).³⁻⁵ Deficits in arm and hand function are commonly found in patients with SPMS and PPMS and can have an impact in performing many activities of daily living. We propose to examine the efficacy of fampridine in upper limb function and in overall disease impact in a single centre, double blind, randomized, placebo-controlled, crossover study of patients attending St Vincent's University Hospital with significant walking and upper limb disability due to SPMS and PPMS.

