9.2 SECONDARY OBJECTIVE

Secondary objectives are:

To assess the effect of treatment with fampridine on walking mobility assessed by the Timed 25 foot Walk (T25FW) and the Multiple Sclerosis Walking Scale (MSWS-12)^{6,7}

To determine whether response or non-response to fampridine by the T25FW can be easily determined using self reported changes in the MSWS-12 alone within 4 weeks in the course of active therapy

To determine whether response or non-response to fampridine by the 9HPT or JTT can be easily determined using self reported changes in the DASH and AMSQ alone within 4 weeks on the course of active therapy

To determine whether any relation exists between improvement / lack of improvement on the T25FW and improvement/ lack of improvement on the 9-HPT or JTT.

To examine the safety of fampridine in this patient population

To assess the impact of fampridine on health related quality of life in patients with multiple sclerosis (HRQOL) as measured by the SF-36 questionnaire.

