10.2 SELECTION OF STUDY POPULATION

Overall description of trial subjects

The study will recruit male and female patients between the ages of 18 – 70 years with clinically definite primary or secondary progressive multiple sclerosis. Patients will be identified in and recruited from the multiple sclerosis clinics in St. Vincent's University Hospital, Dublin, Ireland.

Inclusion criteria

To be eligible for inclusion, each subject must meet each of the following criteria at Screening (Visit 1) and must continue to fulfill these criteria at Baseline (Visit 2).

Subjects must be able and willing to give written informed consent and to comply with the requirements of this study protocol

Subjects must be diagnosed with clinically definite SPMS or PPMS and be judged to be in generally good health by the investigator based upon the results of the medical history, laboratory tests (liver and renal function), physical examination, 12-lead electrocardiogram performed during Screening

Subjects must be Male or female aged 18-70 at baseline

Kurtzke EDSS scores in the range 4.0 to 7.0 inclusive

Evidence of significant upper limb dysfunction as defined by a 9HPT of 15 – 90 seconds (dominant or non-dominant hand)

Female subjects with reproductive capabilities must have a negative serum pregnancy test at baseline and agree to using an acceptable form of contraception for the duration of the study (barrier, coil or oral contraceptives only).

Exclusion criteria

Subjects are excluded from the study if any of the following criteria are met at Screening (Visit 1) or at Baseline (Visit 2):

- Allergy/sensitivity to study medications or their ingredients
- Female subjects who are pregnant or breast-feeding or considering becoming pregnant during the study.
- Subjects unable to provide written informed consent
- Subjects with a history of epilepsy or previous seizures (including provoked seizures).
- Subjects who have a history of drug or alcohol use that, in the opinion of the investigator, would interfere with adherence to study requirements.
- Subjects with an AST or ALT ≥ 3 x ULN on liver function tests
- Subjects have clinically significant ECG findings as judged by the investigator, in particular evidence of a cardiac conduction defect.
- Significant upper or lower limb arthritis as considered by the investigator to interfere with study assessments.
- Significant cognitive impairment as considered by the investigator to interfere with study assessments

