13.5 EFFICACY ANALYSIS

Primary efficacy endpoint:

An upper limb responder to fampridine will be defined as a patient with both of the two "on treatment" 9-HPT assessments (assessments 4 & 5 or 7 & 8) improving 20% from the average of the baseline assessments (1, 2 & 3).

Secondary efficacy endpoints:

- a) A secondary measure of upper limb responsiveness will be defined as a 20% improvement in from baseline in the average time taken to complete all seven tasks on the JTT “on treatment” (assessments 4 & 5 or 7 & 8) compared with baseline assessments (assessments 1,2 & 3).
- b) A mobility responder to dalfampridine will be defined as a patient with both of the two “on treatment” T25FW assessments (assessments 4 & 5 or 7 & 8) being better than the maximum of any of the four “off treatment” assessments (assessments 1, 2, 3, & 9). Otherwise the patient will be deemed a non-responder.
- c) The responders to the 9-HPT and/or JTT will be compared to the non-responders in relation to their changes in the DASH and AMSQ on treatment and off treatment at the baseline assessment. The change in the DASH and AMSQ in responders at Assessment 5 or 8 (week 10 or 20) will be compared to non-responders at that time-point.

Upper limb response will be examined at the end of treatment phase 1 and repeated at the end of the trial by comparing patients receiving active drug with those receiving placebo to assess any placebo effect and allow assessment of any residual beneficial effect on those who receive fampridine in treatment phase 1 and then switch to placebo in treatment phase 2. Response will again be considered as a 20% improvement in the 9HPT in the active treatment group compared with placebo and a 20% improvement from baseline in the time taken to complete all seven tasks in the JTT. See earlier comment

- d) The responders to the T25FW will be compared to the non-responders in relation to their changes in the MSWS-12 on treatment and off treatment at the baseline assessment. The change in the MSWS-12 in responders at Assessment 5 or 8 (week 10 or 20) will be compared to non-responders at that time-point.

The patients’ scores on the MSIS-29 (physical) and SF-36 will be examined in relation to the objective changes (responder/non-responder) in the 9-HPT, JTT and the T25FW.

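### The T25FW responder rule has no class for patients who cannot be timed over 25 feet; read literally it counts them as mobility non-responders, although no entry criterion requires the walk

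*Combined protocol and SAP*

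**What the plan says.** **Entry.** The inclusion criteria in section 10.2 set disability by "Kurtzke EDSS scores in the range 4.0 to 7.0 inclusive". The only timed functional test among them is the 9-HPT, at 15 to 90 seconds. Neither the inclusion nor the exclusion list mentions completing or timing a 25-foot walk. The document history records, for version 2.1, "Defined walking speed removed from inclusion criteria", which agrees with the current list. Section 8.2 describes the intended patients as having "significant walking and upper limb disability due to SPMS and PPMS".

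**Rule.** Section 13.5(b) makes a patient a mobility responder if both on-treatment walks meet the condition of "being better than the maximum of any of the four “off treatment” assessments (assessments 1, 2, 3, & 9"). It then says "Otherwise the patient will be deemed a non-responder". The same rule stands in 9.4 and 10.3.2. The synopsis likewise sorts participants by the T25FW into two classes only.

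**Use.** The class is the grouping variable for the MSWS-12 comparison in 13.5(d) and for the MSIS-29 (physical) and SF-36 comparisons at the end of 13.5. It also underlies two secondary objectives in 9.2: recognising T25FW response from the MSWS-12 within 4 weeks, and "To determine whether any relation exists between improvement / lack of improvement on the T25FW and improvement/ lack of improvement on the 9-HPT or JTT".

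**Missing data.** Section 13.3 makes the primary analysis intention to treat. Section 13.9 bases the primary analysis on complete cases. Neither mentions the T25FW or a test that a patient was unable to do.

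**The concern.** The 9-HPT window in the entry criteria secures a measurable arm baseline. Nothing does the same for the walk. The T25FW rule needs off-treatment walks to beat, and its closing sentence sends everyone else to one class. Two kinds of patient are caught by it:

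- A patient who never completes 25 feet is recorded as not responding in mobility, although mobility response was never measured.
- A patient who completes the walk only on fampridine has no off-treatment value to compare with. The plan gives no code for this, so a real gain may be unscorable or recorded as non-response.

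At stake are the T25FW response rate and every comparison that uses the T25FW class. If the coding is left open, it will be chosen after the data are seen.

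**Working it through.** **Inputs.** From section 13.2: N = 80 and an anticipated response of about 30%. From 8.2: a 7-point MSWS-12 difference, used here for illustration. Assumed, because the documents give no figure: the share u of patients who cannot be timed, shown from 5% to 30%. The plan states no figure on this point that could be reproduced. (The 80 itself cannot be re-derived, since 13.2 gives no power, sidedness or placebo rate; that does not matter here.)

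**1. Response rate and make-up of the non-responder group under the literal rule.** With response r = 0.30 among testable patients:

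reported rate = r(1 − u)

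untestable share of non-responders = 80u / [80 − 80r(1 − u)]

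| u | Untestable | Responders | Reported rate | Untestable share of non-responders |
|---|---|---|---|---|
| 5% | 4 | 22.8 | 28.5% | 4/57.2 = 7% |
| 10% | 8 | 21.6 | 27% | 8/58.4 = 14% |
| 20% | 16 | 19.2 | 24% | 16/60.8 = 26% |
| 30% | 24 | 16.8 | 21% | 24/63.2 = 38% |

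With a separate not-evaluable class, the rate among testable patients stays at 30%.

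**2. MSWS-12 contrast.** Take a 7-point gap between responders and testable non-responders, with the latter unchanged on average. If untestable patients improve by m points, the reported gap is 7 − m × (untestable share of non-responders). At u = 20% (share 0.263):

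- m = 7: 7 − 1.84 = 5.2
- m = 0: 7.0
- m = −7: 7 + 1.84 = 8.8

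**3. Arm-versus-leg relation.** Assume that, among testable patients, arm response is 50% in leg responders and 21.4% in leg non-responders (0.3 × 50% + 0.7 × 21.4% = 30% overall). At u = 20% there are 64 testable patients. The 19.2 leg responders split 9.6 to 9.6 on arm response, and the 44.8 leg non-responders split 9.6 to 35.2. The odds ratio is (9.6/9.6)/(9.6/35.2) = 3.67. Now add the 16 untestable patients to the leg non-responders:

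| Arm response in untestable | Leg non-responders, arm yes : no | Odds ratio |
|---|---|---|
| 0% | 9.6 : 51.2 | 5.33 |
| 21.4% | 13.0 : 47.8 | 3.67 |
| 30% | 14.4 : 46.4 | 3.22 |
| 50% | 17.6 : 43.2 | 2.45 |

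So in steps 2 and 3 the direction of the distortion is not fixed.

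**4. Drug against placebo, paired.** A patient who can be timed in neither period is a non-responder in both, hence a concordant pair. A McNemar-type test uses only discordant pairs. With an illustrative 18 against 4 discordant pairs, the exact p is 0.0043 whether 0, 8 or 16 such patients are added. The absolute difference does shrink: with an assumed 8% placebo response, 22 points becomes 22 × 0.80 = 17.6 at u = 20%.

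**The case against.** **The complete-case rule may drop these patients.** This stands in part. Section 13.9 could be read that way, but it names only the primary analysis, 13.3 says intention to treat, and 13.5(b) is a specific rule with a catch-all. The coding is therefore unsettled. A reader might infer that untestable patients are certain to be counted as drug failures; the documents support that only as the literal reading of 13.5(b).

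**A patient who walks only on drug could be scored a responder.** If the rule is read in terms of speed and inability is set to zero, any completed walk beats it. That is a sensible reading, but the plan does not state it. So it cannot be said that such patients necessarily become non-responders.

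**The affected group is not shown to exist.** The documents do not say what EDSS 7.0 means for walking, and 8.2 speaks of disability, not inability. The removed criterion concerned speed and is not shown to have required ability. Subjects must also satisfy "Subjects must be able and willing to give written informed consent and to comply with the requirements of this study protocol", and the T25FW is scheduled at all nine assessments. This generic criterion gives some protection, though it never mentions walking. The size remains unknown, and nothing in the documents supports the upper end of the range.

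**A responder rate over all randomised patients is legitimate.** Agreed, if it is stated as such. The difficulty is using the same class to explain MSWS-12 change or arm response.

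**A stronger reading to avoid.** A reader might infer that the rule makes arm and leg response look unrelated and dilutes the MSWS-12 contrast. Steps 2 and 3 of the working show that either contrast can be reduced, unchanged or enlarged.

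**Conclusion.** The point holds as a defect in a stated secondary rule. Entry does not require the walk, the rule allows only two classes, and no text says how inability is coded or which of 13.3, 13.5(b) and 13.9 governs. Under the literal rule, and assuming 5% to 30% untestable with 30% response among the rest, the reported T25FW response rate would be 28.5% to 21%, and 7% to 38% of non-responders would be patients who could not be timed. The MSWS-12 and arm-versus-leg contrasts would be distorted by an amount and in a direction that cannot be known beforehand; the MSIS-29/SF-36 comparisons by T25FW class use the same grouping.

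Two limits apply. The primary 9-HPT endpoint does not use this class. A paired drug-placebo test of T25FW response is unchanged by patients who can be timed in neither period. The change should be made, but it does not threaten the trial's main conclusion.

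**What to change.** In 9.4, 10.3.2 and 13.5(b), before the T25FW class is derived:

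1. State the rule in terms of speed. Code a walk that was attempted but not completed as zero, on or off treatment, so that a patient who walks only on treatment can be scored a responder. Distinguish this from a missed visit.
2. Class patients who complete no T25FW at any assessment as not evaluable for mobility. Leave them out of the MSWS-12 comparison, the MSIS-29/SF-36 comparisons by T25FW class and the arm-versus-leg analysis.
3. Require at least one baseline T25FW attempt rather than all three, so that one missed baseline walk does not remove a patient. State what is done when Assessment 9 is missing, since the rule uses it.
4. Report the number not evaluable and the numbers gaining or losing the ability to complete the walk. Keep the coding of all untestable patients as non-responders as a sensitivity analysis.
5. Reconcile 13.5(b) with 13.3 and 13.9, so that one rule decides whether a patient without a T25FW value is classed or dropped.

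The cost is wording, plus a record of whether each walk was attempted and completed; the T25FW is already scheduled at all nine assessments. The downside is slightly fewer patients in the analyses by mobility class.

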Key exclusion criteria	
Patients with a history of seizures, significant liver dysfunction, renal dysfunction, significant upper or lower limb arthritis or any other disorder including cognitive dysfunction which would affect the ability to accurately complete questionnaires and give full informed consent.
 
Patients with clinically significant upper limb ataxia or upper limb proprioceptive sensory loss, which in the opinion of the Clinician affect upper limb functional assessment. Patients concomitantly using medicinal products that are inhibitors of Organic Cation Transporter 2 (OCT2).
 
Patients on concurrent treatment with other medicinal products containing fampridine (4-aminopyridine). Pregnant or breast-feeding patients.

Number of subjects	80
Test product, dose and mode of administration	
Oral PR-Fampridine 10mg b.d
 
Oral Placebo one tablet b.d.

Duration of treatment	Two 8 week treatment periods
Statistical methods	Participants will be classified as to whether they are “responders” or “non-responders” by the 9-HPT and the T25FW according to defined criteria. Change in the MSWS-12, the MSIS-29 (physical) and the DASH and AMSQ in responders and non-responders will be examined by the Wilcoxin Signed Rank test to assess the significance of the mean differences between groups.
Sample size	80

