10.3 STUDY ASSESSMENTS AND PROCEDURES

Patients likely to fulfill the inclusion criteria and not meet any exclusion criteria will be provided with information on the study and invited to attend a subsequent screening visit. Only patients who have signed the informed consent form will participate in any study related procedures including blood testing and ECG.

At screening visit (Assessment 1) subjects will have a physical examination and an EDSS score rated. Blood samples will be taken for renal and liver function and a baseline ECG performed. Patients will complete a nine-hole peg test and a JTT. T25FW will be recorded and the patients invited to complete the MSIS-29, MSWS-12, DASH, AMSQ and SF-36 questionnaires. Patients with any abnormalities on ECG, blood tests will not be invited to a baseline visit and considered a screening failure.

Following screening visit subjects fulfilling the inclusion / exclusion criteria will have two baseline visits (Assessments 2 and 3) at the end of week one and end of week two. The 9-HPT, JTT and T25FW will be repeated to allow for training effects. Patients will be randomised to group A or group B and receive study medication or placebo at baseline visit based on their blinded randomisation (Assessment 3).

The first treatment period will be from the start of week 3 until the end of week 10. Patients will have an assessment at the end of week 6 (Assessment 4) and the end of week 10 (Assessment 5). At both assessments patients will have the 9-HPT, JTT, T25FW, MSIs-29, MSWS-12, DASH, AMSQ and SF-36 recorded. Weeks 11 and 12 will be a washout period (no drug/placebo). Assessment 6 will occur at the end of week 12 and will include recording of 9-HPT, JTT, T25FW, MSIs-29, MSWS-12, DASH, AMSQ and SF-36. Any adverse events will be recorded at each visit as will the use of concomitant medications.

The second treatment period will begin at the start of week thirteen with groups A and B switching study drug / placebo in a blinded manner. The second treatment period will continue for a further 8 weeks with two more assessments at week 16 (Assessment 7) and week 20 (Assessment 8). At both of these assessments subjects will complete the 9-HPT, JTT, T25FW, MSIs-29, MSWS-12, DASH, AMSQ and SF-36. At the end of week 20 and EDSS score will be recorded. Any adverse events will be recorded at each visit as will the use of concomitant medications.

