13.0 STATISTICS

13.1 DESCRIPTION OF STATISTICAL METHODS

Outcome will be assessed using the Wilcoxon Signed Rank test to establish whether there is a difference between the paired 'on treatment' outcome measures for each individual.

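### Two secondary objectives ask whether questionnaires alone can identify responders within 4 weeks, but the plan only compares responder groups and names only 8-week on-treatment visits for this

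*Combined protocol and SAP*

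**What the plan says.** Section 9.2, repeated in the synopsis, sets the two objectives. For the MSWS-12, the question is whether T25FW response "can be easily determined using self reported changes in the MSWS-12 alone within 4 weeks in the course of active therapy". For the upper limb, it is whether 9-HPT or JTT response "can be easily determined using self reported changes in the DASH and AMSQ alone within 4 weeks on the course of active therapy".

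The matching analyses are items (c) and (d) of section 13.5, with the same wording in 9.4 and 10.3.2. Each item has two sentences:

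- The first names no on-treatment visit. For the upper limb, responders are to be "compared to the non-responders in relation to their changes in the DASH and AMSQ on treatment and off treatment at the baseline assessment". Item (d) has the parallel sentence for the MSWS-12.
- The second names visits: "The change in the DASH and AMSQ in responders at Assessment 5 or 8 (week 10 or 20) will be compared to non-responders" and, for walking, "The change in the MSWS-12 in responders at Assessment 5 or 8 (week 10 or 20) will be compared to non-responders".

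On the test, the synopsis says that changes in these questionnaires "will be examined by the Wilcoxin Signed Rank test to assess the significance of the mean differences between groups". Section 13.1 says: "Outcome will be assessed using the Wilcoxon Signed Rank test to establish whether there is a difference between the paired" on-treatment measures.

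On timing, section 10.3 says of the first period: "Patients will have an assessment at the end of week 6 (Assessment 4) and the end of week 10 (Assessment 5"). Assessments 7 and 8 in the second period fall at weeks 16 and 20. The MSWS-12, DASH and AMSQ are scheduled at all four visits.

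**The concern.** The objectives concern individual patients and an early time point: can a clinician rely on a questionnaire, without the timed test, to say by week 4 who is responding? The plan answers a different question: do responders and non-responders differ on average, at a visit that is 8 weeks into treatment?

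No cut-off, sensitivity, specificity, predictive value, ROC analysis or prediction model appears anywhere in the document. If the plan is followed as written, a significant group difference could be read as showing that the questionnaire identifies responders, which it does not show. If a cut-off or visit were instead chosen after unblinding, the reported accuracy would be optimistic.

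**Working it through.** **Timing.** Weeks on treatment = visit week minus the last week before dosing. Section 10.3 starts dosing at the beginning of week 3 and of week 13.

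| Visit | Arithmetic | Weeks on treatment | Named for the questionnaire comparison? |
|---|---|---|---|
| Assessment 4 | 6 − 2 | 4 | No |
| Assessment 5 | 10 − 2 | 8 | Yes |
| Assessment 7 | 16 − 12 | 4 | No |
| Assessment 8 | 20 − 12 | 8 | Yes |

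The visits that match the objectives are 4 and 7. The visits named are 5 and 8.

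**What a significant group difference implies for individuals.** This illustrates a general point. It is not an estimate of how these questionnaires will perform.

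Inputs: 80 patients and about 30% responders (13.2), hence 24 v 56; alpha 0.05 (13.7), taken as two-sided because sidedness is not stated. The 30% in 13.2 refers to a 25% improvement, not the 20% responder definition. Further assumptions: normal change scores with equal variance, an unpaired t-test threshold and a cut midway between the group means.

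- Smallest significant difference: d = t(0.975, 78) × √(1/24 + 1/56) = 1.991 × 0.244 = 0.486 SD
- AUC = Φ(d/√2) = Φ(0.343) = 0.634
- Sensitivity = specificity = Φ(d/2) = Φ(0.243) = 0.596
- PPV = 0.596 × 0.3 / (0.596 × 0.3 + 0.404 × 0.7) = 0.387
- NPV = 0.596 × 0.7 / (0.596 × 0.7 + 0.404 × 0.3) = 0.775

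So the comparison can reach significance while about 61% of the patients flagged as responders are not responders. The NPV is only modestly above the 70% base rate of non-response.

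**Without normality.** For an unpaired rank test, U/(n₁n₂) equals the AUC. With the normal approximation and no ties, the just-significant AUC is 0.5 + 1.96 × √[(n₁ + n₂ + 1)/(12 n₁n₂)]:

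| Responders v non-responders | Assumption | Just-significant AUC |
|---|---|---|
| 24 v 56 | 30% of 80 | 0.639 |
| 19 v 45 | 30% of 64 (20% loss) | 0.656 |
| 8 v 72 | 10% of 80 | 0.712 |

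**Precision of the proposed analysis.** Take an AUC of 0.69. This is the value at the difference detectable with 80% power at 24 v 56: d = (1.960 + 0.842) × 0.244 = 0.684, and Φ(0.684/√2) = 0.686. The Hanley–McNeil 95% half-widths are 0.133 at 24 v 56, 0.149 at 19 v 45 and 0.212 at 8 v 72. In the last case the lower limit is 0.69 − 0.212 = 0.48.

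**The case against.** **Timing.** In 13.5, items (a) and (b) define the on-treatment assessments as 4 and 5 or 7 and 8. Carried forward to the first sentence of (c) and (d), that definition would bring in the 4-week visits, and the Assessment 5 or 8 sentence would be an additional end-of-period comparison. This is a fair reading, and it reduces the timing point to a request for clarification. It does not supply a 4-week analysis, because that sentence is also a comparison of groups.

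**Scope.** Not every analysis in the plan contrasts responders with non-responders. Section 13.1 describes a paired within-patient test, and 13.5 includes an active-versus-placebo comparison. That is true, but neither addresses whether the MSWS-12, DASH or AMSQ identifies a responder.

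**Remedy.** The AUC is the rank statistic rescaled, so it may seem to add little, and individual-level accuracy still needs a cut that the documents do not supply. This stands in part. An AUC with its interval does, however, state how well the questionnaire separates the two groups, which a p-value alone does not.

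**Illustration and importance.** The illustration takes the least favourable significant result and uses a test the plan does not name. That is accepted, and it is offered only to show that significance and classification are different things. Only secondary objectives are affected, and with few responders the added analysis may say little. Both are true and are reflected in the grading.

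**Conclusion.** The concern holds. As written, the plan would not adequately answer two of its six secondary objectives. The method gap is the main fault and does not depend on the visit used: for these questionnaires the plan states only responder-versus-non-responder comparisons, and the only test named is a signed rank test of differences. The timing gap (8 weeks named, 4 weeks asked) may need only a clarifying sentence.

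The textual finding needs no numerical assumption. The accuracy figures rest on the assumed 24 v 56 split, normal change scores and a midpoint cut; the rank-test version drops normality and gives nearly the same AUC. The gap lies in the analysis plan, not in data collection. The change should be made, but it is not critical to the trial's main conclusion.

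**What to change.** Add a 4-week classification analysis to 9.4, 10.3.2 and 13.5 (c) and (d), with matching text in the synopsis and 13.1.

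- **Predictor:** change in MSWS-12, DASH and AMSQ from a pre-randomisation baseline stated in advance (for example the mean of Assessments 1 and 3) to the 4-week visit on active drug. That visit is Assessment 4 for group A and Assessment 7 for group B. For group B, use Assessment 6 as baseline in a sensitivity analysis.
- **Reference:** final responder status on active drug, using T25FW for the MSWS-12, and 9-HPT and JTT separately for the DASH and for the AMSQ. This gives five pairs. T25FW status needs Assessment 9, so say how patients without that visit are handled.
- **Report:** ROC AUC with 95% CI for each pair, labelled as estimation without multiplicity control. Give sensitivity, specificity and predictive values only if an individual cut is fixed before unblinding. The 7-point MSWS-12 figure in 8.2 should not serve as that cut, because it is given there as a difference between groups.
- **Keep** the Assessment 5 or 8 comparison as supportive, and state whether the first sentence of (c) and (d) covers Assessments 4 and 7.

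The cost is text in five places and a little more analysis. The schedule of events already provides the data. The narrative in 10.3 lists only 9-HPT, JTT and T25FW as repeated at the baseline visits; if questionnaires are not in fact taken at Assessment 3, Assessment 1 alone can serve as baseline. The downside is wide intervals: about ±0.13 around an AUC of 0.69 at 24 v 56, and about ±0.21 at 8 v 72, where the analysis would be close to uninformative.
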